# Protocol Details

## Basic Info

Confirmation Number: **bjhhbige**  
Protocol Number: **823896**  
Created By: **[name]**  
Principal Investigator: **[name]**  
Protocol Title: **Ultrasound Assessment of Ventral Hernia Defects**  
Short Title: **ARFI Hernia**  
Protocol Description: **Through the use of ultrasound including sheer wave velocity measurements, the abdominal wall of 25 subjects scheduled to have ventral hernia repair will be compared to those of 25 healthy volunteers. The ultrasound measurements will elucidate if ventral hernia affects abdominal wall elasticity and reveal and effect on surgical outcomes.**  
Submission Type: **Biomedical Research**  
Application Type: **FULL**

## Resubmission\*

Yes

**Responsible Org (Department/School/Division):**

4502 - SU-Surgery Administration

**Disclosure of Significant Financial Interests\***

Does any person who is responsible for the design, conduct, or reporting of this research protocol have a **FINANCIAL INTEREST**?

No

**Penn Intellectual Property\***

To the best of the Principal Investigator's knowledge, does this protocol involve the testing, development or evaluation of a drug, device, product, or other type of intellectual property (IP) that is owned by or assigned to the University of Pennsylvania?

**Certification**

I have reviewed the *Financial Disclosure and Presumptively Prohibited Conflicts for Faculty Participating in Clinical Trials* and the *Financial Disclosure Policy for Research and Sponsored Projects* with all persons who are responsible for the design, conduct, or reporting of this research; and all required Disclosures have been attached to this application.

Yes

## Biomedical Research

**Clinical Trial\***

Is this a clinical trial?

**Investigator Initiated Trial\***

Is this an investigator initiated trial?

No

**Drugs or Devices\***

Does this research study involve Drugs or Devices?

Yes: Investigational devices that may qualify as Non-Significant Risk.

**IND Exemption**

**For studies that fall under an IND exemption, please provide the number below**

**For studies including IND or IDE's, please provide the number(s) below**

**IDE Review\***

NOTE: For research involving investigational devices, you are required to review the guidance on Managing Research Device Inventory. Consult the Penn Manual for Clinical Research: <https://somapps.med.upenn.edu/pennmanual/secure/pm/investigational-product-management> Please check the box Yes if you have reviewed the guidance.

Yes

**Research Device Management\***

Please indicate how research device(s) will be managed.

Not Applicable (no investigational devices)

**Drug, Herbal Product or Other Chemical Element Management \***

Please indicate how drugs, herbal products or other chemical entities will be managed.

Not Applicable (no drugs, herbal products or other chemical entities)

**Radiation Exposure\***

Are research subjects receiving any radiation exposure (e.g. X-rays, CT, Fluoroscopy, DEXA, pQCT, FDG, Tc-99m, etc.) that they would not receive if they were not enrolled in this protocol?

No

**Gene Transfer\***

Does this research involve gene transfer (including all vectors) to human subjects?

No

**Human Source Material\***

Does this research include collection or use of human source material (i.e., human blood, blood products, tissues or body fluids)?

No

**CACTIS and CT Studies\***

Does the research involve Center for Advanced Computed Tomography Imaging Services (CACTIS) and CT studies that research subjects would not receive if they were not part of this protocol?

No

**CAMRIS and MRI Studies\***

Does the research involve Center for Advanced Magnetic Resonance Imaging and Spectroscopy (CAMRIS) and MRI studies that research subjects would not receive if they were not part of this protocol?

No

**Investigational Agent or Device within the Operating Room\***

Does the research project involve the use of an investigational agent or device within the Operating Room?

No

**Cancer Related research not being conducted by an NCI cooperative group\***

Does this protocol involve cancer-related studies in any of the following categories?

No

**Processing of Materials\***

Will the research involve processing (such as over encapsulating, or compounding)?

No

**In-House Manufacturing of Materials\***

Will the research involve processing (such as over encapsulating, or compounding)?

No

**Medical Information Disclosure\***

Does the research proposal involve the use and disclosure of research subject's medical information for research purposes?

Yes

**If the answer is YES, indicate which items is is provided with this submission:**

Modified research informed consent document that incorporates HIPAA requirements

**CTRC Resources\***

Does the research involve CTRC resources?

No

**Pathology and Laboratory Medicine Resources\***

Will samples be collected by hospital phlebotomy and/or processed or analyzed by any of the clinical laboratories of the University of Pennsylvania Health System?

No

**Research Involves Apheresis, Cell Collection, and/or Blood Product Collection\***

Does this research involve collection of blood products in the Penn Donor Center and/or the use of apheresis for treatment or collection of cells or other blood components?

No

**Research involving blood transfusion or drug infusions\***

Will your research involve blood transfusion or infusion of study drug in 3 Ravdin Apheresis Unit for research purposes?

No

**Trial in Radiation Oncology**

Is this research a prospective trial being done in Radiation Oncology, and if so, has this protocol been approved by the Radiation Oncology Protocol committee?

N/A

**Study in Radiation Oncology**

Is this research a retrospective study being done in Radiation Oncology, and if so, has this project been reviewed by the Radiation Oncology Clinical Research Group?

N/A

**Use of UPHS services\***

Does your study require the use of University of Pennsylvania Health System (UPHS) services, tests or procedures\*, whether considered routine care or strictly for research purposes?

Yes

**Primary Focus\***

Clinical Trial (prospectively assigning subjects to health-related interventions to evaluate outcomes)

**Protocol Interventions**

**Sociobehavioral (i.e. cognitive or behavioral therapy)**

**Drug**

**Device - therapeutic**

**Device - diagnostic (assessing a device for sensitivity or specificity in disease diagnosis)**

**Surgical**

**Diagnostic test/procedure (research-related diagnostic test or procedure)**

**Obtaining human tissue for basic research or biospecimen bank**

**Survey instrument**

**None of the above**

**The following documents are currently attached to this item:**

*There are no documents attached for this item.*

**Department budget code**

None

# Multi-Site Research

## Other Sites

No other sites

## Management of Information for Multi-Center Research

na

## The following documents are currently attached to this item:

*There are no documents attached for this item.*

# Protocol

## Abstract

Quantitative radiographic imaging holds promise as a novel and innovative strategy to assess ventral hernia patients. We will identify features of the abdominal wall that differ between healthy volunteers and subjects scheduled to have ventral hernia repair. We will assess abdominal wall changes surrounding ventral hernia using shear wave velocity values measured with ultrasound. Up to 25 subjects previously diagnosed with ventral hernia seeking surgical repair will receive ultrasound prior to repair and following repair and will be compared to up to 25 healthy volunteers.

## Objectives

### Overall objectives

Identify characteristic changes in the abdominal wall associated with ventral hernia. Determine elasticity of the abdominal wall in subjects known to have a hernia defect to those who are determined to have normal abdominal wall anatomy.

### Primary outcome variable(s)

Sheer wave velocity measurements in the abdominal wall.

### Secondary outcome variable(s)

Identification of any association between muscular elasticity/stiffness of the abdominal and surgical data/outcomes of the hernia repair.

## Background

Significance of hernia and magnitude of the problem: Two million abdominal surgeries are performed annually in the United States, and ventral hernia (VH) is among the most common and serious complications(1, 2). The incidence of VH is approximately 13%(3), but as high as 70% in high-risk populations(1, 4-8). Despite improving surgical treatment strategies and mesh technology, long-term success rates of VH repair remain unacceptably low. The 348,000 VH repairs performed in 2006 cost over \$3 billion (2). As a result of recurrence and morbidity, a disproportionately small subset (15%) of patients consumes more than 50% of expenditures(9), and become caught in the vicious cycle of hernia recurrence and morbidity. Failed repairs generate un-closable midline defects that require mesh bridging, meaning that native fascia cannot be closed and that mesh is bridged across the fascia. Bridging is a relevant and clinically meaningful outcome that occurs during the repair and has significant implications since these repairs fail in 44 to 100% of cases and are associated with significant cost (8, 10-13). Patients suffering from recurring hernia experience deterioration in quality- of-life, significant disability, and dysfunction; if un-closable defects can be identified using a point-of- care technology peri-operative decision-making could be substantially improved. Role of imaging in hernia care: There are currently no reliable data, standard imaging modalities, or guidelines available to predict successful fascial closure in hernia repair, which represents a substantial gap in knowledge and barrier to progress (4, 14-16). Surgeons are unable to adequately counsel patients and preoperatively plan complex VH repairs, which presents a clinical dilemma. The current state of hernia repair relies heavily on clinical evaluation of patients, which, as stated, is ultimately a poor predictor of patient outcome going into surgery for hernia repair. Additionally, there is a dearth of data regarding the use of various imaging modalities to diagnose and predict hernia outcomes of any kind. As of today, the only

recommended radiologic technique for the evaluation of hernia is CT, a costly and ultimately ineffective measure (17). If a technique leveraging the strengths of ultrasound (US) could be developed, it would be far superior to other modalities in terms of cost, time, and patient safety (Table 1) (18). There is little evidence regarding the role of ultrasound performed by surgeons in the diagnosis of hernias of any type. Clearly, hernia ultrasound has the potential to be highly useful for surgical practice, however a well-designed trial needs to be carried out(14). Hernia leads to abdominal wall muscle fibrosis and decreased compliance, which presents an opportunity to quantify this change using specialized imaging techniques. Muscle fibrosis impedes closure (leading to bridging), and unloaded skeletal muscle undergoes architectural atrophic changes such as altered fiber composition, diminished cross-sectional area, and fibrosis that has been shown to be detectable and quantifiable (19, 20). Quantitative imaging using Acoustic Radiation Forced Impulse Shear Wave Velocity (ARFI-SWV) holds promise as a novel and innovative strategy to assess skeletal muscle pathology(21), and has already proven useful in evaluating fibromuscular disorders by quantitating stiffness and fibrosis (21, 22). Hernia repair outcomes are likely impacted by morphological changes that occur in the abdominal wall when significant fibrosis occurs. Clinically relevant target features include abdominal wall muscle thickness, pre-existing defects in the abdominal wall, or assessment of mechanical characteristics of muscular layers such as fibrosis or fatty infiltration (19, 20, 23). Clinical Implications and Future Directions: Completing this study will provide an opportunity to advance the applications of ARFI-SWV US imaging modalities for risk prediction of complex VH defects, translating this tool into the clinic as a point-of-care prognostic aid. The ability to preoperatively identify un-closable hernia defects represents an innovative strategy to an unmet clinical need with the potential to greatly impact thousands of patients. Following this critical, inter-disciplinary pilot, our team will have a reproducible and reliable quantitative tool. This translational research of proven concepts across multiple medical fields represents a significant collaborative effort and is just the first step that will be the foundation for future studies. The results of this proposal will be used to refine a protocol for preoperative shear wave velocity assessment in complex VH patients. The proposed translational research study represents a strong and promising collaborative effort between radiology, biomedical imaging, and surgery that will build upon recent work and cutting edge technology, setting in motion future research opportunities. The NIH states, The success of a potential shift from curative medicine, to predictive, personalized, and preemptive medicine could rely on the development of portable diagnostic and monitoring devices for point-of-care testing(25). It is with this notion in mind that we propose this work. We hope to develop a point-of-care technique that will allow the surgeon to pre-operatively assess the outcome of surgery at the bedside. Establishing a point-of-care test will allow surgeons to personalize their approach to each patient and avoid submitting patients to the spiral of hernia recurrence and morbidity. References 1. Candise R, Jones K, Luchette FA, Sinacore JM, Vandevender D, Reed RL, 2nd. Use of human acellular dermal matrix for hernia repair: friend or foe? *Surgery*. 2008;144(4):703-9; discussion 9-11. Epub 2008/10/14. doi: 10.1016/j.surg.2008.06.018. PubMed PMID: 18847657. 2. Poulose BK, Shelton J, Phillips S, Moore D, Nealon W, Penson D, et al. Epidemiology and cost of ventral hernia repair: making the case for hernia research. *Hernia*. 2012;16(2):179-83. doi: 10.1007/s10029-011-0879-9. PubMed PMID: 21904861. 3. Bosanquet DC, Ansell J, Abdelrahman T, Cornish J, Harries R, Stimpson A, et al. Systematic Review and Meta-Regression of Factors Affecting Midline Incisional Hernia Rates: Analysis of 14 618 Patients. *PLoS One*. 2015;10(9):e0138745. doi: 10.1371/journal.pone.0138745. PubMed PMID: 26389785; PubMed Central PMCID: PMCPMC4577082. 4. Franklin BR, Patel KM, Nahabedian MY, Baldassari LE, Cohen EI, Bhanot P. Predicting abdominal closure after component separation for complex ventral hernias: maximizing the use of preoperative computed tomography. *Ann Plast Surg.* 2013;71(3):261-5. Epub 2013/08/16. doi: 10.1097/SAP.0b013e3182773915 00000637-201309000-00004 [pii]. PubMed PMID: 23945530. 5. Chavarriaga LF, Lin E, Losken A, Cook MW, Jeanssonne LO, White BC, et al. Management of complex abdominal wall defects using acellular porcine dermal collagen. *Am Surg*. 2010;76(1):96-100. PubMed PMID: 20135948. 6. Le Huu Nho R, Mege D, Ouaissi M, Sielezneff I, Sastre B. Incidence and prevention of ventral incisional hernia. *J Visc Surg*. 2012;149(5 Suppl):e3-14. Epub 2012/11/13. doi: 10.1016/j.jviscsurg.2012.05.004. PubMed PMID: 23142402. 7. Veljkovic R, Protic M, Gluhovic A, Potic Z, Milosevic Z, Stojadinovic A. Prospective clinical trial of factors predicting the early development of incisional hernia after midline laparotomy. *J Am Coll Surg*. 2010;210(2):210-9. Epub 2010/02/02. doi: 10.1016/j.jamcollsurg.2009.10.013. PubMed PMID: 20113942. 8. Basta MN, Fischer JP, Kovach SJ. Assessing complications and cost-utilization in ventral hernia repair utilizing biologic mesh in a bridged underlay technique. *Am J Surg*. 2015;209(4):695-702. Epub 2014/10/13. doi: 10.1016/j.amjsurg.2014.04.017. PubMed PMID: 25305799. 9. Poulose BK, Beck WC, Phillips SE, Sharp KW, Nealon WH, Holzman MD. The chosen few: disproportionate resource use in ventral hernia repair. *Am Surg*. 2013;79 (8):815-8. PubMed PMID: 23896251. 10. Itani KM, Rosen M, Vargo D, Awad SS, Denoto G, 3rd,


## Study Design

### Phase\*

Not applicable

### Design

Proposed Study Aims: Creating a protocol and using an existing technology to enhance informed risk counseling at the point-of-care will empower surgeons to personalize their approach to each patient, enhancing the informed decision process, fostering greater patient autonomy, and improving quality of care (24). ARFI-SWV US holds promise as an inexpensive, noninvasive, point-of-care diagnostic tool for pre-operatively predicting successful repair at the bedside. We will measure abdominal wall features suitable for predicting successful closure of the midline fascia. To accomplish these goals, we propose the following aims: Aim 1. To develop and refine a quantitative ultrasound protocol to assess mechanical changes in abdominal tissue. ARFI-SWV US represents a novel and intriguing modality for

real time visualization and characterization of changes in the biomechanical properties of diseased musculoskeletal tissues. We hypothesize that ARFI-SWV US can be used preoperatively to measure the stiffness in the lateral abdominal wall as an estimation for mobility during hernia repair. Demonstrating the utility of a cheap, point-of-care test for preoperatively evaluating hernia severity will prove to be a valuable, novel tool in surgical assessment of ventral hernia patients. Aim 2. To perform a prospective pilot ARFI-SWV US assessment of abdominal wall characteristics that predicts success of midline fascial re-approximation in hernia patients. A prospective comparative analysis of preoperative ARFI- SWV US exams in patients undergoing hernia repair (N=25) will be performed. We hypothesize that fibrosis and other identifiable mechanical characteristics of the abdominal wall musculature can predict ability to close fascia in VH patients. Preoperative identification of ultrasound features characteristic of severe hernia defects can be used to predict which hernias will be un-closable, resulting in poorer outcomes. The study proposes to compare ultrasound images and associated shear wave velocity measurements between healthy subjects and subjects undergoing surgical repair for ventral hernia. We will compare up to 25 healthy volunteers with up to 25 ventral hernia subjects. Any female patients of child-bearing age will be asked to take a urine pregnancy test prior to being included in the study at the time of consent. Subjects with ventral hernia will undergo imaging no earlier than two weeks prior to elective hernia repair and within six months following repair at a standard followup visit. Medical information related to their hernia or hernia repair from these subjects will remain available for analysis for the duration of the study. Statistical analysis will determine if there is a significant difference in the abdominal wall stiffness, represented by the ultrasound shear wave velocity measurements, between the healthy subjects and the subjects with ventral hernia. Further analysis will determine if there is any statistically significant relationship between abdominal wall stiffness of subjects with ventral hernia and surgical outcomes, including bridged repairs, as well as any change in abdominal wall stiffness following ventral hernia repair.

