### **Analysis Plan**

Analysis will include comparing shear wave velocity measurements between healthy subjects and subjects with ventral hernia as well as correlating these measurements with the surgical outcome/data among patients with ventral hernia. Further, we will compare the measurements taken in subjects who underwent hernia repair before and after the hernia repair.

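### Aim 2 asks whether stiffness predicts un-closable fascia, but the plan tests only for an association, which does not measure discrimination

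*Combined protocol and SAP*

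**What the plan says.** The Design section frames Aim 2 as prediction. It announces: "We will measure abdominal wall features suitable for predicting successful closure of the midline fascia". It hypothesises that "identifiable mechanical characteristics of the abdominal wall musculature can predict ability to close fascia in VH patients", and adds that preoperative ultrasound features "can be used to predict which hernias will be un-closable, resulting in poorer outcomes". The Background expects the team to hold a reliable quantitative tool once the pilot is finished.

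The analysis is described in three places, each time as association:

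- Design: "Further analysis will determine if there is any statistically significant relationship between abdominal wall stiffness of subjects with ventral hernia and surgical outcomes". Bridged repairs are named there among the outcomes.
- Analysis Plan: "correlating these measurements with the surgical outcome/data among patients with ventral hernia".
- Secondary outcome variable(s): "Identification of any association between muscular elasticity/stiffness of the abdominal and surgical data/outcomes of the hernia repair".

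The other two planned comparisons, hernia versus healthy and before versus after repair, do not concern closure. The protocol gives no AUC, sensitivity, specificity, predictive value, cut-off, confidence interval, validation step, alpha or expected number of bridged repairs for Aim 2.

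The sample is "patients undergoing hernia repair (N=25) will be performed", and that number is a ceiling: "We will compare up to 25 healthy volunteers with up to 25 ventral hernia subjects".

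**The concern.** A prediction question needs a measure of how far the readings of un-closable patients lie from those of closable ones, and how much the two overlap. A test for a relationship answers a weaker question: whether the data are consistent with no link at all. A low p-value can go with heavy overlap. With few bridged repairs, a high one can go with a useful test.

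If the plan is followed exactly, Aim 2 ends without any estimate of discrimination. A surgeon could not learn from it how much to rely on a reading. A team planning the next study would lack the effect size and precision that a pilot should supply.

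**Working it through.** The plan states no power, alpha, effect size or bridging rate for Aim 2, so there is no figure of its own to reproduce.

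**Inputs**
- N = 25 hernia patients (Design, Aim 2). Healthy volunteers have no repair outcome and do not contribute.
- Two-sided alpha 0.05: assumed.
- Number of bridged repairs k: assumed, 3 to 12. The Background gives a failure rate for bridged repairs (44 to 100%), not how often bridging occurs.
- Model: normal readings with equal variance in the two groups, assumed only to translate significance into discrimination.

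**Step 1: effect size at p = 0.05.** With 23 degrees of freedom the critical t is 2.069, so d = 2.069 × √(1/k + 1/(25 − k)). For k = 5, d = 2.069 × √(0.20 + 0.05) = 2.069 × 0.5 = 1.03.

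**Step 2: convert to AUC.** AUC = Φ(d/√2). For k = 5, Φ(1.03/1.414) = 0.77.

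**Step 3: interval.** At p = 0.05 the lower limit of d is 0, which gives AUC 0.50. The upper limit comes from the noncentral t distribution. For k = 5 it is d = 2.05, so AUC = Φ(2.05/1.414) = 0.93.

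| Bridged / 25 | d | AUC | 95% interval for AUC |
|---|---|---|---|
| 3 | 1.27 | 0.82 | 0.50 to 0.96 |
| 5 | 1.03 | 0.77 | 0.50 to 0.93 |
| 8 | 0.89 | 0.73 | 0.50 to 0.89 |
| 10 | 0.84 | 0.72 | 0.50 to 0.88 |
| 12 | 0.83 | 0.72 | 0.50 to 0.88 |

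**Step 4: other routes.**
- Exact Mann-Whitney test: the smallest significant result gives AUC 0.80 at 5/25 (logit-scale interval 0.46 to 0.95), 0.75 at 8/25 (0.48 to 0.91) and 0.74 at 10/25 (0.49 to 0.89).
- Correlation: the just-significant r is 2.069/√(23 + 2.069²) = 0.396, so R² = 0.16, with a Fisher-z interval of 0.001 to 0.684.

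**Step 5: the reverse error.** Under the same model a true AUC of 0.80 (d = √2 × 0.842 = 1.19) reaches significance about 63% of the time with 5 bridged repairs and about 46% with 3. A non-significant result would not rule out a useful test.

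**Step 6: precision of the proposed estimate.** Using the Hanley-McNeil standard error at a true AUC of 0.75, the 95% half-width with N = 25 is about 0.27, 0.23 and 0.21 at bridging rates of 20%, 30% and 40%. A half-width of 0.10 would need about 174, 125 and 103 patients.

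**The case against.** This is a secondary outcome in a study that calls itself a pilot and a first step, and patients receive their standard treatment whatever the scan shows. Looking for an association first is conventional. That limits the seriousness, and it stands. It does not supply the missing estimate: a pilot meant to found later studies needs an effect size with its uncertainty.

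An interval that touches the null at p = 0.05 is a property of any just-significant result at any sample size. That also stands. What 25 patients add is the width of the interval above the null.

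The documents do not support four stronger readings that a reader might infer:

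- *A p-value below 0.05 would be reported as prediction.* No section gives a reporting rule. The word belongs to the aims and hypotheses, while the outcome and analysis wording is association.
- *The plan compares group means.* No test is named. A rank-sum test is itself a test of AUC against 0.5, and logistic regression models the probability of the outcome. The t-test above is only a way of showing scale.
- *Most flagged patients would be false alarms.* This depends on the unstated bridging rate. At a cut-off with 80% sensitivity, specificity is Φ(d − 0.842). At 5/25 that is 58%, with a positive predictive value of 32% and a negative predictive value of about 92%. The positive predictive value rises to 52% at 10/25 and 59% at 12/25.
- *The scan is useless.* The same intervals include strong discrimination.

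**Conclusion.** The point holds as a mismatch between question and analysis: Aim 2 is posed as prediction, and the plan yields no measure of discrimination. With at most 25 hernia patients, a just-significant relationship would be compatible with anything from about chance to an AUC of roughly 0.9 or higher, so it would not settle the question either way.

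The size rests on an assumed two-sided alpha of 0.05, an assumed 3 to 12 bridged repairs and the equal-variance normal model. The conclusion is the same across that range and by the rank-based route. Fewer than 25 patients would make the precision worse. The primary comparison of hernia with healthy subjects is not affected.

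**What to change.** 1. Keep the association analysis. It serves the stated secondary outcome and the other surgical data, such as defect size, components separation and complications.
2. Add to the Analysis Plan, for bridged versus closed fascia, the AUC of preoperative lateral-wall shear wave velocity with a 95% confidence interval by a named small-sample method. Make this the exploratory main estimate for Aim 2.
3. Report any sensitivity and specificity with exact intervals, as descriptive only. A fixed 80% sensitivity target is not workable here: with 3 bridged repairs the observed sensitivity can only be 0, 33, 67 or 100%. Even 5 of 5 detected has an exact lower 95% limit of 0.48 (0.025^(1/5)).
4. Label any cut-off chosen from these data as unvalidated.
5. Word the Aim 2 conclusion as an association, or a preliminary estimate of discrimination, to be validated in a later study. Bring the Background's expectation of a reliable tool into line with this.

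The cost is a few sentences and a few lines of code. The preoperative readings and the surgical outcomes are already to be collected, so no further patients, scans or visits are needed. The downside is a wide interval and a less favourable conclusion.
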